6.1. Timing of Assessments

Study procedures will be performed in accordance with the following schedule (see also Table 2 – Theoretical Schedule of Visits and Acceptable Leeway):

Day -15 to Day -1: screening and baseline assessment

Then, depending on the type of patient:

Patients treated in hospital:

Treatment period: Day 1 to Day 10

EoT visit: Day 11

■ EoH visit: between Day 13 and Day 18

Patients on an out-patient basis:

IMP dispensing visit prior to first intake of IMP: Day 0

Compulsory EoT visit at investigational centre: Day 11

Out-patient follow-up visits for all patients:

• 3 months, 6 months, 12 months and 18 months

The schedule of visits is calculated from the first day of treatment (Day 1).

Confidential Page 32 of 83

Table 2 - Theoretical Schedule of Visits and Acceptable Leeway

Type of Visit	Schedule of Visits and Acceptable Time Window	Acceptable leeway*
EoT Visit	Day 11	Day 11 + 1 day
End-of-Hospitalisation Visit, only for patients treated in hospital	Between Day 13 and Day 18	Day 18 at the latest
3-month follow-up visit	3 months ± 1 week after Day 1	2 to 4 months, i.e. 60 to 149 days, after Day 1
6month follow-up visit	6 months ± 1 week after Day 1	5 to 9 months, i.e. 150 to 299 days, after Day 1
12-month follow-up visit	12 months ± 4 weeks after Day 1	10 to 16 months, i.e. 300 to 509 days, after Day 1
18-month follow-up visit	18 months ± 4 weeks after Day 1	17 to 21 months, i.e. 510 to 659 days, after Day 1

^{*} The acceptable leeway for the visit starts on the first day of the period mentioned and ends on the last day of the period mentioned.

Additional unscheduled visits may take place and must be recorded in the CRF. See also Appendix 7 - Schedule of Study Events (p 82).

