6.8.3. Follow-up on AEs

Any AE must be followed up until it resolves, until the Investigator considers it to be "stable" or "chronic", or until the end of the patient's participation in the study, i.e. until the end-of-study page of the CRF for the patient has been completed.

If the AE is a clinically significant laboratory test abnormality, a repeat test is to be performed 2 to 4 days later and then at regular intervals until the value returns to normal or to the baseline level.

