#### Time-windows:

The timing of follow-up visits is calculated from the first day of treatment (D1).

The table below defines the theoretical schedule of follow-up visits and the acceptable Leeway:

Type of visit	Schedule of visit and ideal timing of visits	Acceptable Leeway*
End-of-hospitalisation (EoH) visit, only for patients treated in hospital	Between D13 and D18 after D1	D18 at the latest
3 months	3 months $\pm$ 1 week after D1	2 to 4 months, i.e. 60 to 149 days, after Day 1
6 months	6 months $\pm$ 1 weeks after D1	5 to 9 months, i.e. 150 to 299 days, after Day 1
12 months	12 months $\pm$ 4 weeks after D1	10 to 16 months, i.e. 300 to 509 days, after Day 1
18 months	18 months $\pm$ 4 weeks after D1	17 to 21 months, i.e. 510 to 659 days, after Day 1

\* The acceptable leeway for the visit starts on the first day of the period mentioned and ends on the last day of the period mentioned.

Any additional unscheduled visits that may take place must be recorded in the CRF. Real timing of unscheduled visits will be calculated and they will be analysed in the corresponding time-window (see table above).

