#### **8.8.3. Laboratory examination**

For continuous data, a descriptive analysis will be provided for baseline, at each time point and for the changes from baseline at each time point, by cohorts, subgroups and overall.

Changes in blood levels over time will be presented in graphs.

Shift tables between baseline severity (normal value, abnormal not clinically significant, abnormal clinically significant) and severity at each timepoint (i.e. D5, D11, M3, M6, M12, M18) for each laboratory parameters will be provided by cohorts, subgroups and overall.

Scattergrams between baseline value and value at each timepoint (i.e. D5, D11, M3, M6, M12, M18), for each laboratory parameters will be provided by cohorts, subgroups and overall.

Proportions of patients by category corresponding to the size of the increase in relation to the ULN for liver function tests (i.e. ALT, AST, total bilirubin and alkaline phosphatase) will be described (< 1 ULN, 1–2 ULN, 2–3 ULN etc.) by cohorts, subgroups and overall.

A listing of patients with clinically significant abnormalities in laboratory parameters will be provided (cf. [Section 9.1](#)).

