## 8.11. Unscheduled visit

During the data review, any efficacy and safety data from unscheduled visit which must be taken into account in the analysis will be identified.

Other data from unscheduled visits will only be tabulated in listings except for time to event analyses where they will be taken into account.

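### The laboratory-value tables run by named timepoint with no worst post-baseline value, so a transient liver or blood peak at a retest or unscheduled test can be missing from them.

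*Protocol*

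**What the plan says.** **Windows.** Protocol Table 2 gives the end-of-treatment visit on Day 11 with one day of leeway. The end-of-hospitalisation visit, for in-patients only, runs from Day 13 to "D18 at the latest". The next window, for the 3-month visit, is "2 to 4 months, i.e. 60 to 149 days, after Day 1". SAP 7.5 repeats this table without the end-of-treatment row.

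**Tests that fall between visits.** Under Protocol 6.8.3, an adverse event that is a clinically significant laboratory finding triggers retesting: "a repeat test is to be performed 2 to 4 days later and then at regular intervals until the value returns to normal". A return to baseline also ends the retesting. Protocol 6.7.3 also allows haematology and biochemistry at any unscheduled visit, at the investigator's discretion.

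**Tables.** SAP 8.8.3 builds shift tables between baseline and "severity at each timepoint (i.e. D5, D11, M3, M6, M12, M18) for each laboratory parameters", uses the same timepoints for scattergrams, and describes continuous values at each timepoint. A further table sorts liver tests by multiple of the ULN; no timepoint is named for it.

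**Unscheduled values.** SAP 7.5 says of unscheduled visits that "they will be analysed in the corresponding time-window (see table above"). SAP 8.11 has the data review identify the unscheduled efficacy and safety data that must be used. For the rest: "Other data from unscheduled visits will only be tabulated in listings", apart from time-to-event analyses.

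**The concern.** The protocol generates laboratory values at times for which the SAP has no column. A retest after an abnormal Day 11 result lands in a stretch with no laboratory timepoint, and a test prompted by symptoms during dosing has no window either. One SAP rule sends such values to a corresponding window that does not exist. The other sends them to listings unless the data review selects them, and gives no criterion for selection.

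With no worst post-baseline summary, a value that rises and falls between Day 11 and Month 3 can leave the shift and CTCAE tables looking clean. Protocol 1.4 reports liver reactions and transient, asymptomatic grade 3 and 4 neutropenia with this drug in another disease, which is the pattern that by-visit tables are poorly suited to show. In an open-label, single-arm study the maximum grade and the proportion above each ULN multiple are central descriptive safety results, and they should not depend on case-by-case selection.

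**Working it through.** **1. Reproduce the window limits.** With 30-day months, the lower limit is 30 × first month and the upper limit is 30 × (last month + 1) − 1.
- 3 months: 30 × 2 = 60; 30 × 5 − 1 = 149
- 6 months: 150 to 299
- 12 months: 300 to 509
- 18 months: 510 to 659

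All agree with Table 2, and from day 60 the windows run without a break.

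**2. Find the uncovered days.** Laboratory tests are scheduled at baseline, Day 11 (+1), Month 3 and Month 6, and at Months 12 and 18 if clinically indicated.
- Days 13 to 59: 59 − 13 + 1 = 47 days with no laboratory timepoint.
- For in-patients, the end-of-hospitalisation window covers Days 13 to 18, leaving 59 − 19 + 1 = 41 days with no visit window. But Protocol 6.7.1 lists no laboratory test at that visit, and SAP 8.8.3 does not name it as a laboratory timepoint.
- Days 1 to 10: no laboratory window. The SAP names D5, but neither protocol schedule (Tables 5 and 6) has a laboratory test that day and SAP 7.5 gives it no window.

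**3. Place the mandated retest.** A repeat 2 to 4 days after a test on Day 11 falls on Days 13 to 15; after Day 12, on Days 14 to 16. Both ranges lie wholly in the gap.

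**4. One constructed patient.** Protocol Appendix 6 gives an ALT ULN of 61 U/L, grade 1 up to 183 and grade 3 from above 305 to 1220.

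| Test | ALT (U/L) | Multiple of ULN | Grade |
|---|---|---|---|
| Day 11 | 150 | 150/61 = 2.5 | 1 |
| Day 14 retest | 400 | 400/61 = 6.6 | 3 |
| Month 3 | 45 | 45/61 = 0.7 | none |

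The CTCAE shift table shows grade 1 at D11 and nothing at M3. The grade 3 value has no column.

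**5. Size in the laboratory-value tables.** The documents give no rate of such peaks, so the number of patients is assumed. Exact (Clopper-Pearson) 95% intervals, n = 174:

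| Patients at grade ≥ 3 only at such tests | True proportion (95% CI) | Shown in by-visit tables |
|---|---|---|
| 1 | 0.6% (0.0 to 3.2) | 0/174 (0 to 2.1) |
| 5 | 2.9% (0.9 to 6.6) | 0/174 (0 to 2.1) |
| 10 | 5.7% (2.8 to 10.3) | 0/174 (0 to 2.1) |

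The upper limit for 0/174 is 1 − 0.025^(1/174) = 2.1%. The last column assumes that no other patient reaches grade 3 at a scheduled visit and that the data review brings none of these values in.

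**6. Follow the adverse-event route.** SAP 6.3 analyses as AEs only those laboratory abnormalities that investigators report as AEs. TEAEs run from first intake to Month 18 with no gap (SAP 6.3.1). SAP 8.8.2 counts patients with a severe TEAE overall and within cohorts and subgroups. Its SOC and preferred-term tables cover all, drug-related, serious, and serious drug-related TEAEs, none of them by grade. Under Protocol 6.8.4, non-serious events after Day 11 (out-patients) or the end-of-hospitalisation visit (in-patients) are collected only if judged related.

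**The case against.** A reader might infer that a peak found at a retest enters no safety table at all, and that the trial would report 0/174 in place of 5/174. The documents do not support that.
- The retest rule in Protocol 6.8.3 applies to an abnormality that is already an AE. The patient in step 4 would be in the AE data set, graded and followed, and a grade 3 event belongs in the severe-TEAE row.
- An abnormality that leads to stopping the drug counts as clinically significant under Protocol 6.8.1, and SAP 8.8.2 tabulates TEAEs leading to discontinuation. ALT or AST above 3 ULN with bilirubin above 2 ULN is an SAE.
- The liver-category sentence names no timepoint, so it does not exclude retest values.
- SAP 8.11 lets the data review bring unscheduled values in, tests from day 60 have a window, and clinically significant abnormalities are listed.
- Table 2 sets visit leeways. With no visit planned between Days 19 and 59, the absence of a window there is not itself a defect.
- The protocol's stated focus on haematological and hepatic function (section 1.6) concerns data at 3 and 6 months, and nothing in the documents says that peaks occur just after Day 11.

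All of this stands, and it confines the point to the laboratory-value tables. It does not remove it. AE status rests on the investigator's judgement of clinical significance. A non-serious grade 3 ALT rise or leukopenia cannot be identified by parameter and grade in any planned table. That the liver table is silent on its timepoint means it does not assure inclusion either, and two programmers could produce different tables from the same text.

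**Conclusion.** The point holds for the laboratory-value tables: by-visit summaries, shift tables, CTCAE shifts and scattergrams. Days 13 to 59 have no laboratory timepoint, unscheduled tests on Days 1 to 10 have no window, SAP 7.5 and 8.11 conflict, and no worst post-baseline value is defined. What can be lost from every table is the numeric peak, abnormalities not reported as AEs, and non-serious abnormalities that first arise after the AE collection period and are judged unrelated.

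The proportions in step 5 illustrate the laboratory-value tables only and rest on assumed counts; they are not a forecast of the trial's reported safety. The primary endpoint is unaffected. This is a cheap improvement.

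**What to change.** In SAP 8.8.3, and in Tables 3.2.1.3, 3.2.1.4 and 3.2.1.6 with their biochemistry copies:
- Add a worst post-baseline column per patient: the maximum CTCAE grade and, for liver tests, the maximum multiple of ULN. Use all scheduled, repeat and unscheduled values from first intake through the Month 3 visit.
- State that the liver-category table uses this maximum as well as the by-visit values.
- Reconcile SAP 7.5 with 8.11, so that one rule says where an unscheduled value goes when no window covers it.
- Keep the by-visit tables as they are.

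The cost is SAP wording and one extra column in existing tables. No new data or visits are needed, because these values are already collected and due to be listed. The downside is that patients tested more often have more chances of an extreme value, so reported rates become slightly less favourable; a footnote can say so.

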6.2. Screening and Baseline Assessment

6.2.1. Screening

Patients who are to participate in the study will be recruited either through active screening, i.e. patients already diagnosed by the mobile teams and referred to the investigational centre, or through passive screening, i.e. patients diagnosed at the investigational centre or nearby.

- In the context of active screening, the mobiliser of the mobile team will inform the communities in the villages of the HAT screening activities, as is usually the case (see Section 14.1 Information of the Communities; p 59). Specific information concerning the study will be provided to the community, i.e. a brief description of the aim of the study, explanation of the process for collecting informed consent, duration and importance of follow-up.
- In the context of passive screening, specific information concerning the study will be provided by static healthcare structures located near the investigational centre in order to refer patients to the investigational centre.

Confidential Page 33 of 83

Diagnosis of HAT and staging of the disease will be performed at the investigational centre.

The following diagnostic tests will be performed at the investigational centre between Day -15 and Day -1 to confirm the diagnosis of HAT:

- Serological testing (RDT or CATT);
- Collection of blood and/or lymph samples for testing for parasites;

If a patient has been diagnosed as HAT-positive in the context of another clinical study sponsored by DNDi, the results of diagnostic tests, i.e. blood and/or lymph samples or lumbar puncture, can be used in the present study if they were performed less than 7 days before Screening.

Patients will be invited to participate in the study and the Investigator (or a designee) will provide the information required to collect the patient's informed consent. Once the patient has signed the informed consent, s/he will be considered as a "screened patient" and s/he will receive a patient ID number.

6.2.2. Baseline Assessment

Whether the patient is being considered for treatment in hospital or as an out-patient, the following procedures will be performed between Day -15 and Day -1 in order to stage the disease, to collect medical history and safety data, and to check the inclusion and non-inclusion criteria.

- Collection of informed consent / assent prior to administering any additional medication or to performing any non-routine assessment;
- Collection of CSF sample for WBC and disease staging;
- Karnofsky Performance Status,
- Review of inclusion and non-inclusion criteria
- Collection of demographic data;
- Collection of full medical history;
- Collection of signs and symptoms of HAT, in particular severity and time since the start of symptoms;
- Vital signs: body temperature, blood pressure, heart rate and respiratory rate;
- Diagnosis of malaria using RDT and/or thick blood smear and, if the result is positive, administration of antimalarial treatment;
- Treatment of helminthiasis, according to routine practices;
- Collection of concomitant medication;
- Physical and neurological examinations;

Confidential Page 34 of 83

- Laboratory safety assessments (see Appendix 3 Laboratory Tests; p 75) when possible, samples will be collected in the morning from patients in the fasting state;
 - Haemoglobin;
 - o Haematology: WBC, platelet count;
 - Biochemistry: albumin, alkaline phosphatase (ALP), alanine aminotransferase (ALT), aspartate aminotransferase (AST), blood urea nitrogen (BUN), chloride, creatinine, glucose, potassium, sodium, calcium, total bilirubin, bicarbonates and total protein;
 - Urine analysis (leucocytes, nitrites, pH, protein, glucose, ketone bodies, urobilinogen, bilirubin, blood and haemoglobin);
- Urine pregnancy test for women of child-bearing potential, to be done on Day -1;
- Triplicate digital ECG (CarTouch®), to be done on Day -1;
- Collection of SAEs.

6.3. IMP Dispensing: Day 0

If the patient is to be treated on an out-patient basis, the following procedures will be performed before s/he returns home to begin treatment.

- Check that all procedures for baseline assessment have been performed.
- Dispensing of IMP and, before returning home, reminder concerning instructions for taking the IMP and interview with Investigator to collect responses to questionnaire and ensure good understanding of the instructions by the patient and/or the caregiver;
- Collection of SAEs since signature of informed consent.

6.4. Procedures during Treatment Period for Patients Treated In Hospital: Day 1 to Day 10

6.4.1. Clinical Signs and Symptoms

- Patients will be questioned each day concerning possible AEs during the hospitalisation period and at each subsequent follow-up visit (see Section 6.8 Safety Assessments, Definitions; p 40);
- Collection of concomitant medication.

If indicated by the patient's clinical status, the following procedures will be performed on Day 8:

Vital signs: body temperature, blood pressure, heart rate and respiratory rate;

Confidential Page 35 of 83

Physical and neurological examinations.

6.4.2. ECG Recordings

Two digital ECGs (CarTouch®) will be recorded in triplicate to assess QT-interval:

- 4 hours after intake of IMP on Day 4;
- 23 hours after intake of IMP, i.e. 1 hour before intake of IMP on Day 5.

6.4.3. PK Analyses

The procedure for sampling and the assay method will be described in the Laboratory Manual.

During the treatment phase, four samples will be collected for PK analyses.

Whole blood, approximately 2 mL each time, collected by venipuncture will be deposited on filter paper using the dry blood spot (DBS) technique at the following timepoints:

Table 3 – PK Sampling Times during the Treatment Period

Ideal timing for sample collection	Acceptable leeway
Day 8: 3 hours 15 minutes after intake of the IMP	± 15 min
Day 9: 3 hours after intake of the IMP	± 15 min
Day 10: 3 hours and 7 hour 15 minutes after intake of the IMP	± 15 min

6.5. Treatment Period for Patients Treated on an Out-patient Basis

Patients treated on an out-patient basis who require hospitalisation, for whatever reason, will undergo the same procedures as patients initially treated in hospital, up to the end of the hospitalisation period, as provided for in the protocol. During this period, and up to Day 13 or Day 18, the reasons for hospitalisation will not be considered to be SAEs solely based on the criterion of hospitalisation, but may be considered to be SAEs based on other criteria (see Section 6.8.1).

PK sampling should be performed at any unscheduled visit between Day 1 and Day 10, regardless of the day on which the visit takes place.

Confidential Page 36 of 83

6.6. Procedures at the EoT Visit – Day 11

Whether the patient is being treated in hospital or as an out-patient, the following procedures will be performed at the EoT visit on Day 11:

- Collection of blood and/or lymph samples for testing for parasites;
- Collection of signs and symptoms of HAT, if any;
- Karnofsky Performance Status;
- Vital signs: body temperature, blood pressure, heart rate and respiratory rate;
- Physical and neurological examinations;
- Collection of concomitant medication and AEs;
- Urine pregnancy test for women of child-bearing potential;
- Laboratory safety assessments (see Appendix 3 Laboratory Tests; p 75) when possible, samples will be collected in the morning from patients in the fasting state;
 - Haemoglobin;
 - Haematology: WBC, platelet count;
 - o Biochemistry: albumin, ALP, ALT, AST, BUN, chloride, creatinine, glucose, potassium, sodium, calcium, total bilirubin, bicarbonates and total protein;
 - Urine analysis (leucocytes, nitrites, pH, protein, glucose, ketone bodies, urobilinogen, bilirubin, blood and haemoglobin);
- Triplicate digital ECG (CarTouch®);
- Collection of blood sample 24 hours after the last intake of the IMP (Day 11) for PK analyses. If the patient was treated on an out-patient basis, the sample will be used to check treatment compliance. If the patient was treated in hospital, a second blood sample will be collected 48 hours (Day 12) after the last intake of the IMP for PK analyses.

Table 4 - PK Sampling Times at the End of the Treatment Period

Ideal timing for sample collection	Acceptable leeway
Day 11: 24 hours after the last intake of the IMP	± 1 hour
Day 12: 48 hours after the last intake of the IMP (only for patients treated in hospital)	± 1 hour

Confidential Page 37 of 83

If the patient was treated on an out-patient basis, the following procedures will be performed:

- Interview for collection of AEs observed by the patient during the treatment period and collection of concomitant medication;
- Interview for compliance with accountability of fexinidazole tablets;
- Questionnaire to assess acceptability of packaging of IMP.

6.7. Procedures at Follow-up Visits

6.7.1. Procedures at EoH Visit - Day 13 to Day 18

If the patient was treated in hospital, the following procedures will be performed on the day of discharge:

- Vital signs: body temperature, blood pressure, heart rate and respiratory rate;
- Physical and neurological examinations;
- Collection of concomitant medication and AEs.

6.7.2. Procedures at Follow-up Visits at 3, 6, 12 and 18 months

Whether the patient is being treated in hospital or as an out-patient, the following procedures will be performed at Follow-up Visits at 3, 6, 12 and 18 months:

- Collection of blood and/or lymph samples for testing for parasites;
- Collection of CSF for WBC and detection of trypanosomes. At the 3-month follow-up visit, lumbar puncture will be performed only if indicated by the patient's clinical status;
- Collection of signs and symptoms of HAT, if any;
- Karnofsky Performance Status;
- Vital signs: body temperature, blood pressure, heart rate and respiratory rate;
- Physical and neurological examinations;
- Urine pregnancy test for women of child-bearing potential, only at 3-month and 6-month visits;
- Collection of SAEs
- Collection of non-serious AEs assessed as related to fexinidazole;
- Laboratory safety assessments (see Appendix 3 Laboratory Tests; p 75) when possible, samples will be collected in the morning from patients in the fasting state:
 - Haemoglobin;
 - Haematology: WBC, platelet count;

Confidential Page 38 of 83

o Biochemistry: albumin, ALP, ALT, AST, BUN, chloride, creatinine, glucose, potassium, sodium, calcium, total bilirubin, bicarbonates and total protein.

Laboratory safety assessments will be performed at the 12-month and 18-month visits only if indicated by the patient's clinical status.

In the event that a patient moves house or is travelling away from home during the follow-up period, the Investigator accompanied by any necessary study team members may travel to the patient's new place of residence in order to perform one or more follow-up visits.

The patient could also attend one or more follow-up visits in another investigational centre or in a satellite centre. The patient would then be managed by the Investigator in the other investigational centre or by the Coordinating Investigator at the PNLTHA.

The site investigator and his/her study team can also travel to the satellite site to monitor the patient.

In that case, the Investigator in the patient's original investigational centre should inform the Coordinating Investigator and the person in charge of monitoring that a visit is planned to take place in a different investigational centre.

Data collected at such visits will then be sent, within a reasonable timeframe after the visit, to the patient's original investigational centre in order to be recorded in the CRF.

The patient's original investigational centre is responsible for entry of the data and retains medical responsibility for the patient.

